7.2.2 Reporting of Pregnancy and Lactation to the Sponsor

Although pregnancy and lactation are not considered adverse events, it is the responsibility of investigators or their designees to report any pregnancy or lactation in a subject (spontaneously reported to them) that occurs during the trial.

Protocol/Amendment No.: 004-02

Pregnancies and lactations that occur after the consent form is signed but before treatment allocation/randomization must be reported by the investigator if they cause the subject to be excluded from the trial, or are the result of a protocol-specified intervention, including but not limited to washout or discontinuation of usual therapy, diet, placebo treatment or a procedure. Pregnancies and lactations that occur from the time of treatment allocation/randomization through 14 days following cessation of Sponsor's product must be reported by the investigator. All reported pregnancies must be followed to the completion/termination of the pregnancy. Pregnancy outcomes of spontaneous abortion, missed abortion, benign hydatidiform mole, blighted ovum, fetal death, intrauterine death, miscarriage and stillbirth must be reported as serious events (Important Medical Events). If the pregnancy continues to term, the outcome (health of infant) must also be reported.

Such events must be reported within 24 hours to the Sponsor either by electronic media or paper. Electronic reporting procedures can be found in the EDC data entry guidelines. Paper reporting procedures can be found in the Investigator Trial File Binder (or equivalent).

7.2.3 Immediate Reporting of Adverse Events to the Sponsor

7.2.3.1 Serious Adverse Events

A serious adverse event is any adverse event occurring at any dose or during any use of Sponsor's product that:

- Results in death;
- Is life threatening;
- Results in persistent or significant disability/incapacity;
- Results in or prolongs an existing inpatient hospitalization;
- Is a congenital anomaly/birth defect:
- Is a cancer;
- Is associated with an overdose;
- Is an other important medical event

Refer to Table 10 for additional details regarding each of the above criteria.

For the time period beginning when the consent form is signed until treatment allocation/randomization, any serious adverse event, or follow up to a serious adverse event, including death due to any cause, that occurs to any subject must be reported within 24 hours to the Sponsor if it causes the subject to be excluded from the trial, or is the result of a protocol-specified intervention, including but not limited to washout or discontinuation of usual therapy, diet, placebo treatment or a procedure.

For the time period beginning at treatment allocation/randomization through 14 days following cessation of treatment, any serious adverse event, or follow up to a serious adverse event, including death due to any cause, whether or not related to the Sponsor's product, must be reported within 24 hours to the Sponsor either by electronic media or paper. Electronic reporting procedures can be found in the EDC data entry guidelines. Paper reporting procedures can be found in the Investigator Trial File Binder (or equivalent).

Additionally, any serious adverse event, considered by an investigator who is a qualified physician to be related to the Sponsor's product that is brought to the attention of the

Protocol/Amendment No.: 004-02

investigator at any time outside of the time period specified in the previous paragraph also must be reported immediately to the Sponsor.

All subjects with serious adverse events must be followed up for outcome.

7.2.3.2 Events of Clinical Interest

Selected non-serious and serious adverse events are also known as Events of Clinical Interest (ECI) and must be reported to the Sponsor.

For the time period beginning when the consent form is signed until treatment allocation/randomization, any ECI, or follow up to an ECI, that occurs to any subject must be reported within 24 hours to the Sponsor if it causes the subject to be excluded from the trial, or is the result of a protocol-specified intervention, including but not limited to washout or discontinuation of usual therapy, diet, placebo treatment or a procedure.

For the time period beginning at treatment allocation/randomization through 14 days following cessation of treatment, any ECI, or follow up to an ECI, whether or not related to the Sponsor's product, must be reported within 24 hours to the Sponsor, either by electronic media or paper. Electronic reporting procedures can be found in the EDC data entry guidelines. Paper reporting procedures can be found in the Investigator Trial File Binder (or equivalent).

Events of clinical interest for this trial include:

- 1. an overdose of Sponsor's product, as defined in Section 7.2.1 Definition of an Overdose for This Protocol and Reporting of Overdose to the Sponsor, that is not associated with clinical symptoms or abnormal laboratory results.
- 2. an elevated AST or ALT lab value that is greater than or equal to 3X the upper limit of normal and an elevated total bilirubin lab value that is greater than or equal to 2X the upper limit of normal and, at the same time, an alkaline phosphatase lab value that is less than 2X the upper limit of normal, as determined by way of protocol-specified laboratory testing or unscheduled laboratory testing.*
 - *Note: These criteria are based upon available regulatory guidance documents. The purpose of the criteria is to specify a threshold of abnormal hepatic tests that may require an additional evaluation for an underlying etiology. The trial site guidance for assessment and follow up of these criteria can be found in the Investigator Trial File Binder (or equivalent).
 - 3. Any subject meeting HR discontinuation criteria (see Section 5.9).

7.2.4 Evaluating Adverse Events

An investigator who is a qualified physician will evaluate all adverse events with respect to the elements outlined in Table 10. The investigator's assessment of causality is required for each adverse event. Refer to Table 10 for instructions in evaluating adverse events.

Product: MK-8521 81

Protocol/Amendment No.: 004-02

Table 10 Evaluating Adverse Events

Maximum	Mild awareness of sign or symptom, but easily tolerated (for pediatric trials, awareness of symptom, but easily tolerated)					
Intensity						
	Severe incapacitating with inability to work or do usual activity (for pediatric trials, extremely distressed or unable to do usual activities)					
Seriousness	A serious adverse event (AE) is any adverse event occurring at any dose or during any use of Sponsor's product that:					
	†Results in death	r; or				
	†Is life threatening; or places the subject, in the view of the investigator, at immediate risk of death from the event as it occurred [Note: This does not include an adverse event that, had it occurred in a more severe form, might have caused death.]; or †Results in a persistent or significant disability/incapacity (substantial disruption of one's ability to conduct normal life functions); or					
	†Results in or prolongs an existing inpatient hospitalization (hospitalization is defined as an inpatient admission, regardless of length of s hospitalization is a precautionary measure for continued observation. (Note: Hospitalization for an elective procedure to treat a pre-existing condition worsened is not a serious adverse event. A pre-existing condition is a clinical condition that is diagnosed prior to the use of a Merck product and is do patient's medical history.); or					
I	†Is a congenital anomaly/birth defect (in offspring of subject taking the product regardless of time to diagnosis); or					
	Is associated with an overdose (whether accidental or intentional). Any adverse event associated with an overdose is considered a serious adverse event. An overdose that is not associated with an adverse event is considered a non-serious event of clinical interest and must be reported within 24 hours.					
	Other important medical events that may not result in death, not be life threatening, or not require hospitalization may be considered a serious adve based upon appropriate medical judgment, the event may jeopardize the subject and may require medical or surgical intervention to prevent one of the previously (designated above by a †).					
Duration	Record the start and stop dates of the adverse event. If less than 1 day, indicate the appropriate length of time and units					
Action taken	Did the adverse event cause the Sponsor's product to be discontinued?					
Relationship to Sponsor's Product	ponsor's investigator who is a qualified physician. The investigator's signed/dated initials on the source document or worksheet that support					
	based upon the available information					
	The following co	mponents are to be used to assess the relationship between the Sponsor's product and the AE; the greater the correlation with the components				
	and their respective	and their respective elements (in number and/or intensity), the more likely the Sponsor's product caused the adverse event:				
	Exposure Is there evidence that the subject was actually exposed to the Sponsor's product such as: reliable history, acceptable compliance assessment (grant of the subject was actually exposed to the Sponsor's product such as: reliable history, acceptable compliance assessment (grant of the subject was actually exposed to the sponsor's product such as: reliable history, acceptable compliance assessment (grant of the subject was actually exposed to the sponsor's product such as: reliable history, acceptable compliance assessment (grant of the subject was actually exposed to the sponsor's product such as: reliable history, acceptable compliance assessment (grant of the subject was actually exposed to the sponsor's product such as: reliable history, acceptable compliance assessment (grant of the subject was actually exposed to the sponsor's product such as: reliable history, acceptable compliance assessment (grant of the subject was actually exposed to the sponsor's product such as: reliable history, acceptable compliance assessment (grant of the subject was actually exposed to the sponsor's product such as: reliable history, acceptable compliance assessment (grant of the subject was actually exposed to the sponsor's product such as: reliable history, acceptable compliance assessment (grant of the subject was actually exposed to the sponsor's product such as a sponsor of the subject was actually exposed to the sponsor of the subject was actually exposed to the sponsor of the subject was actually exposed to the sponsor of the subject was actually exposed to the sponsor of the sponsor of the sponsor of the subject was actually exposed to the sponsor of the spon					
		count, diary, etc.), expected pharmacologic effect, or measurement of drug/metabolite in bodily specimen?				
	Time Course	Did the AE follow in a reasonable temporal sequence from administration of the Sponsor's product?				
		Is the time of onset of the AE compatible with a drug-induced effect (applies to trials with investigational medicinal product)?				
	Likely Cause Is the AE not reasonably explained by another etiology such as underlying disease, other drug(s)/vaccine(s), or of factors					

Product: MK-8521

Protocol/Amendment No.: 004-02

Relationship	The following components are to be used to assess the relationship between the Sponsor's product and the AE: (continued)			
to Sponsor's	Dechallenge	Was the Sponsor's product discontinued or dose/exposure/frequency reduced?		
Product		If yes, did the AE resolve or improve?		
(continued)		If yes, this is a positive dechallenge. If no, this is a negative dechallenge.		
		(Note: This criterion is not applicable if: (1) the AE resulted in death or permanent disability; (2) the AE resolved/improved		
	continuation of the Sponsor's product; (3) the trial is a single-dose drug trial); or (4) Sponsor's product(s) is/are only used one time.)			
	Rechallenge Was the subject re-exposed to the Sponsor's product in this trial?			
	If yes, did the AE recur or worsen?			
		If yes, this is a positive rechallenge. If no, this is a negative rechallenge.		
		(Note: This criterion is not applicable if: (1) the initial AE resulted in death or permanent disability, or (2) the trial is a single-dose drug trial);		
		or (3) Sponsor's product(s) is/are used only one time.)		
		NOTE: IF A RECHALLENGE IS PLANNED FOR AN ADVERSE EVENT WHICH WAS SERIOUS AND WHICH MAY HAVE BEEN		
		CAUSED BY THE SPONSOR'S PRODUCT, OR IF RE-EXPOSURE TO THE SPONSOR'S PRODUCT POSES ADDITIONAL POTENTIAL		
		SIGNIFICANT RISK TO THE SUBJECT THEN THE RECHALLENGE MUST BE APPROVED IN ADVANCE BY THE SPONSOR		
	G : 4	CLINICAL DIRECTOR AND THE INSTITUTIONAL REVIEW BOARD/INDEPENDENT ETHICS COMMITTEE.		
	Consistency with Trial	Is the clinical/pathological presentation of the AE consistent with previous knowledge regarding the Sponsor's product or drug class		
	Treatment	pharmacology or toxicology?		
	Profile			
The assessment of		reported on the case report forms /worksheets by an investigator who is a qualified physician according to his/her best clinical judgment, including		
consideration of th		reported on the case report forms, worksheets by an investigation who is a quantitied physician according to institute judgment, moratuming		
Record one of the		Use the following scale of criteria as guidance (not all criteria must be present to be indicative of a Sponsor's product relationship).		
Yes, there is a rea	acanabla	There is evidence of exposure to the Sponsor's product. The temporal sequence of the AE onset relative to the administration of the Sponsor's		
possibility of Sponsor's product		product is reasonable. The AE is more likely explained by the Sponsor's product than by another cause.		
relationship.		product is reasonable. The ris is more metry expansed by the sponsor oproduct than by another enable.		
No, there is not a reasonable		Subject did not receive the Sponsor's product OR temporal sequence of the AE onset relative to administration of the Sponsor's product is not		
possibility of Sponsor's product		reasonable OR there is another obvious cause of the AE. (Also entered for a subject with overdose without an associated AE.)		
relationship				

Protocol/Amendment No.: 004-02

7.2.5 Sponsor Responsibility for Reporting Adverse Events

All Adverse Events will be reported to regulatory authorities, IRB/IECs and investigators in accordance with all applicable global laws and regulations.

7.3 TRIAL GOVERNANCE AND OVERSIGHT

7.3.1 Executive Oversight Committee

The Executive Oversight Committee (EOC) comprises members of Sponsor Senior Management. The EOC will receive and decide upon any recommendations made by the standing internal Data Monitoring Committee (siDMC) regarding the trial.

7.3.2 Data Monitoring Committee

To supplement the routine monitoring outlined in this protocol, a separate Standing Internal Data Monitoring Committee (siDMC) will review any interim data that is triggered by prespecified safety criteria or is conducted for administrative planning purposes. The siDMC comprises members of Sponsor Senior Management, none of whom are directly associated with the conduct of this trial. The siDMC will monitor the trial at an appropriate frequency (see Section 8.1.4 and Section 8.2.9 - Interim Analyses) for evidence of adverse effects of trial treatment, as described in the detailed monitoring guidelines. In addition to the trigger based siDMC review, an interim analysis will be performed when at least 50% of the subjects have either completed Week 12 or have discontinued the study. The planned interim analysis will be performed for the purpose of determining whether interim efficacy and safety data justify continuation of the study conduct (potential termination for futility), and, if study continuation is warranted, to consider sample size re-estimation (refer to Section 8.2.9) based on assessment of variance. When an interim analysis is performed, the siDMC will review the data and provide guidance based on criteria detailed in the siDMC charter. The siDMC will determine whether the trial should continue (or other modifications, pre-specified or otherwise, should be made) according to the protocol, considering the overall risk and benefit to trial participants. The siDMC will also make recommendations to the Sponsor protocol team regarding steps to ensure both subject safety and the continued ethical integrity of the trial.

Specific details regarding responsibilities of the siDMC will be described in a separate charter that is reviewed and approved by the siDMC.

8.0 STATISTICAL ANALYSIS PLAN

8.1 Statistical Analysis Plan Summary

This section contains a brief summary of the statistical analyses for this trial. Full detail is in the Statistical Analysis Plan (SAP) (Section 8.2).

8.1.1 Efficacy Analysis

The primary and key secondary efficacy endpoints, primary analysis population, and statistical methods that will be employed for the efficacy analyses are presented in Table 11 below.

Product: MK-8521

Protocol/Amendment No.: 004-02

Table 11 Summary of Analysis Strategy for Key Efficacy Endpoints

Endpoint	Statistical Method	Analysis Population	Missing Data Approach
Primary efficacy endpoint: A1C – Change from baseline at Week 12	cLDA	FAS	Model-based
Body Weight – Change from baseline at Week 12	cLDA	FAS	Model-based
Fasting Plasma Glucose – Change from baseline at Week 12	cLDA	FAS	Model-based

For the primary efficacy analyses, a constrained longitudinal data analysis (cLDA) method proposed by Liang and Zeger [22] will be used. The cLDA model will include terms for treatment (4 arms), time, stratification factors of A1C (<8.5%, $\ge8.5\%$), BMI (<30 kg/m2, ≥30 kg/m2) and AHA washout status (Yes, No), and the interaction of time by treatment, with the restriction of a common baseline mean across treatment groups. An unstructured covariance matrix will be used to model the correlation among repeated measurements.

The primary comparisons for efficacy endpoints are each of the MK-8521 doses versus placebo. The primary population for all efficacy analyses will be the Full Analysis Set (FAS), comprised of all subjects who received at least one dose of trial therapy and have a baseline measurement or a post-randomization measurement.

8.1.2 Safety Analysis

The All-Subjects-as-Treated (ASaT) population will be used for safety analyses. Safety and tolerability will be assessed following a tiered approach by clinical review of all relevant parameters including AEs, laboratory tests, vital signs, and ECG. For safety endpoints designated as Tier 1 (adverse events of symptomatic hypoglycemia), p-values and 95% CIs for between-treatment differences (each of the two doses of MK-8521 versus placebo and versus liraglutide) will be provided.

8.1.3 Power and Sample Size

Approximately 160 subjects will be randomized in a 1:1:1:1 ratio to 300 μg dose and 180 μg dose of MK-8521, MK-8521 placebo or liraglutide. After 12 weeks of MK-8521, a reduction of $\geq 0.8\%$ in A1C and ≥ 2 kg in body weight, relative to placebo, is expected. This sample size will provide approximately 85% power to detect a true difference of 0.8% in the mean change from baseline in A1C between a MK-8521 dose and placebo at the 2-sided 0.05 significance level. The same sample size will provide approximately 87% power to detect a true difference of 2 kg in body weight between a MK-8521 dose and placebo. The same sample size will also provide approximately 88% power to detect a true difference of 30 mg/dL in FPG. The sample size may be increased as a result of the interim analysis. Details are provided in Section 8.2.9.

8.1.4 Interim Analysis

In the event of ≥ 5 subjects discontinuing blinded investigational product (MK-8521 or matching placebo) due to meeting the defined discontinuation criteria for an increase in HR, a review of unblinded safety data by the siDMC will be triggered. An siDMC review may also be triggered for other potentially important safety signals from the blinded ongoing

Protocol/Amendment No.: 004-02

safety results identified during medical monitoring, to be detailed in a separate siDMC charter.

In addition to the trigger-based safety review, an interim analysis will be performed for the purpose of determining whether interim efficacy and safety data justify continuation of the study. If not, study termination for futility will be considered. If the study is not terminated, an additional goal will be sample size re-estimation based on assessment of variance (described in Section 8.2.9). The results of this interim analysis will be reviewed by the siDMC.

The endpoints, timing, and purpose of the interim analysis are summarized in Table 14 in Section 8.2.9. An unblinded statistician and programmer not associated with the day-to-day conduct of the study will provide unblinded information to the siDMC. The approach to the interim analysis is described in more detail in Section 8.2.9.

8.2 Statistical Analysis Plan

8.2.1 Responsibility for Analyses/In-House Blinding

The statistical analysis of the data obtained from this study will be the responsibility of the Clinical Biostatistics department of the SPONSOR. This study will be conducted as a double-blind study under in-house blinding procedures. At the end of the trial, the official, final database will be frozen and unblinded after medical/scientific review has been performed, protocol violators have been identified (if applicable), and data have been declared final and complete.

As discussed in Section 8.1.4 and Section 8.2.9, an interim analysis will be performed to assist in the MK-8521 development program planning (including earlier initiation of planning for subsequent studies of MK-8521 and/or of dual peptide back-up programs) and to terminate the study for futility or to adjust the sample size, as warranted. It is expected that most of the planned 160 subjects will have been randomized at the time of the interim analysis. Blinding to treatment assignment will be maintained at all investigational sites. Results of interim analyses will not be shared with the Investigators prior to the completion of the study. Subject-level unblinding will include an internal unblinded statistician and scientific programmer performing the interim analysis, who will have no other responsibilities associated with the study. The results of this interim analysis will be reviewed by the siDMC. If interim data are felt to warrant consideration of administrative action with regard to other aspects of the development program or if study termination is under consideration due to meeting futility criteria, the unblinded interim data will be reviewed with additional individuals with programmatic oversight. Individuals directly involved with study conduct will not be unblinded until the end of the study.

If, after the trial has begun, but prior to any unblinding, changes are made to primary hypotheses and/or key secondary hypotheses, or the statistical methods related to those hypotheses, then the protocol will be amended (consistent with ICH Guideline E-9). No separate Statistical Analysis Plan (SAP) will be issued for this trial.

The Clinical Biostatistics department will generate the randomized allocation schedule for study treatment assignment. Randomization will be implemented in an interactive voice response system (IVRS).

Protocol/Amendment No.: 004-02

8.2.2 Hypotheses

Objectives and hypotheses of the study are stated in Section 3.

8.2.3 Analysis Endpoints

Efficacy and safety endpoints that will be evaluated for within- and/or between-treatment differences are listed below.

The primary time point of the study is Week 12.

The baseline value will be defined as the **Visit 3/Day 1** (Randomization) measurement. If this measurement is not available, the following pre-randomization measurement will be used as the baseline value.

Regimen at Visit 1/Screening	Baseline value		
On metformin monotherapy (no washout)	If the Visit 3 measurement is missing, the Visit 1 measurement will be used. If neither measurement is available, the baseline value will be treated as missing		
On dual therapy metformin and a second AHA (enter washout)	If the Visit 3 measurement is missing, the Visit 2 measurement will be used. If neither measurement is available, the baseline value will be treated as missing		

The mapping of relative day ranges to Week is provided in Section 12.4.

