- Subjects on dual AHA therapy (metformin plus a second permissible AHA) will proceed to Visit 1A, at which time they will receive diet and exercise counseling and initiate washout of the non-metformin agent. The washout period will be at least 8 weeks, after which they will proceed to Visit 2/Week -2 and enter a 2 week placebo run-in period. If they continue to meet eligibility criteria, randomization will occur at Visit 3/Day 1.

Eligibility for continued study participation will be assessed at Visits 1, 2, and 3 (Randomization/Day 1) based on the criteria detailed in Section 5.1. For subjects for whom Visit 2 occurs more than 2 weeks after Visit 1 (including all subjects undergoing washout), this includes the requirement, that A1C at Visit 2 be \geq 7.5% and \leq 10.5% (\geq 58 mmol/mol and \leq 91 mmol/mol) and that required laboratory results (see Flow Chart, Section 6.0) are consistent with enrollment criteria.

Note: If Visit 2 occurs \leq 2 weeks after Visit 1, then repeat A1C and screening laboratories should **not** be conducted.

The placebo run-in may be initiated at Visit 2/Week -2 while laboratory data, including A1C, are pending, but randomization may not occur until all eligibility criteria are confirmed. If a subject has initiated the placebo run-in but screen fails due to A1C or other laboratory data collected at Visit 2, they should be contacted and told to discontinue the placebo run-in.

For subjects who meet enrollment criteria at Visit 1 except for elevated triglycerides (TG) and/or elevated blood pressure, the investigator may initiate or adjust lipid-lowering and/or blood pressure medication and permit the subject to proceed with pre-randomization activities. **Note the following for these subjects:**

- All modification of lipid-lowering and/or blood pressure medication must occur prior to Visit 2/Week -2 (with unscheduled visits, as needed).
- Lipid-lowering and/or blood pressure medications must be at a stable dose for at least 4 weeks prior to Visit 3/randomization. The screening period (Visit 1 to Visit 2) should be extended as necessary to meet this requirement.

Protocol/Amendment No.: 004-02

• Subjects for whom lipid-lowering medication is initiated or modified to address elevated TG must meet TG eligibility criteria at Visit 2 to proceed to randomization. All subjects must meet blood pressure eligibility criteria at Visit 3/randomization to proceed with randomization.

Placebo Run-In

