5.4 Stratification

Randomization will be stratified according to the following factors:

- 1. A1C*: <8.5% or $\ge 8.5\%$
- 2. BMI*: $<30 \text{ kg/m}^2 \text{ or } \ge 30 \text{ kg/m}^2$
- 3. AHA washout status: yes or no.

*The Visit 1/Screening value will be used for stratification if Visit 2/Week -2 occurs ≤2 weeks of Visit 1/Screening. The Visit 2/Week -2 value will be used for stratification if Visit 2/Week -2 is >2 weeks after Visit 1/Screening (this will include all subjects undergoing AHA washout).

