- u. Women of childbearing potential will have a urine pregnancy test (and serum pregnancy test if required by site's Institutional Review Board [IRB]/Ethics Committee [EC]). Subjects with a positive urine pregnancy test during the treatment period will interrupt investigational product and undergo a serum pregnancy test.
- v. Subjects on metformin monotherapy who meet all Visit 1/Screening eligibility criteria can proceed directly to Visit 2/Week -2. Subjects on metformin monotherapy who meet all Visit 1/Screening eligibility requirements except for TG and/or blood pressure criteria should have initiation or adjustment of lipid-lowering/blood pressure medication made prior to Visit 2/Week -2, with unscheduled visits, as needed. The screening period (Visit 1 to Visit 2) should be extended so that subjects are on a stable regimen for at least 4 weeks

Protocol/Amendment No.: 004-02

prior to Visit 3/Day 1.

- w. Only subjects who are on dual therapy with metformin and a second AHA will perform **Visit 1A/Washout**. Allowable AHAs for washout at **Visit 1A/Washout** include: DPP-4 inhibitors, α-glucosidase inhibitors, sulfonylureas and glinides.
- x. Performed at Visit 2/Week -2 only if Visit 2/Week -2 occurs >2 weeks after Visit 1/Screening.
- y. Not applicable for Visit 2/Week -2 if these items were already dispensed/performed at Visit 1A/Washout.
- z. Only applicable for subjects who did not satisfy the Visit 1/Screening TG criterion. A fasting TG sample should not be obtained for subjects who satisfied the Visit 1/Screening TG criterion.
- aa. Subjects should be reminded to not to take any other AHA medications other than metformin and randomized therapy (MK-8521/placebo or open-label liraglutide) during their participation in the study. They should be counseled that if another physician prescribes such a treatment (i.e., any AHA), the subject and/or the prescribing physician should immediately contact the investigational site prior to initiation of such therapy (unless alternative AHA therapy is considered clinically to be immediately required). Subjects who were washed off of another AHA should be reminded to remain off this agent while participating in the current trial, and to not re-start this agent post-study unless advised by their diabetes care-giver (whether the investigator or another physician).

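### For metformin-monotherapy subjects, a missing Visit 3 baseline falls back to Visit 1 even when a later pre-dose Visit 2 value was collected

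*Combined protocol and SAP*

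**What the plan says.** Section 8.2.3 defines baseline as the Visit 3/Day 1 measurement and gives a two-row fallback table keyed to the regimen at screening.

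- Metformin monotherapy, no washout: "If the Visit 3 measurement is missing, the Visit 1 measurement will be used". If neither exists, baseline is missing.
- Dual therapy, entering washout: "If the Visit 3 measurement is missing, the Visit 2 measurement will be used". If neither exists, baseline is missing.

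Section 5.4 uses a different key, the interval between Visits 1 and 2, to choose the A1C and BMI values for stratification: "The Visit 2/Week -2 value will be used for stratification if Visit 2/Week -2 is >2 weeks after Visit 1/Screening". That covers every subject with the longer interval, washout or not. Footnote x of the flow chart (Section 6.0) applies the same interval to repeating A1C, chemistry and hematology at Visit 2.

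The plan expects some monotherapy subjects to have a long interval. Footnote v reads: "Subjects on metformin monotherapy who meet all Visit 1/Screening eligibility requirements except for TG and/or blood pressure criteria should have initiation or adjustment" of the relevant medication before Visit 2. It continues: "The screening period (Visit 1 to Visit 2) should be extended so that subjects are on a stable regimen for at least 4 weeks" before Visit 3. Section 2.1 agrees on timing: "All modification of lipid-lowering and/or blood pressure medication must occur prior to Visit 2/Week -2".

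**The concern.** A baseline should be the closest available measurement before the first dose. The monotherapy row passes over Visit 2, which is nearer to dosing than Visit 1 and, for some measurements, is already in the database. Three consequences follow.

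- In a monotherapy subject with extended screening, the A1C stratum comes from Visit 2 while the fallback baseline comes from the older Visit 1. Both enter the same cLDA model.
- In a subject who failed the Visit 1 triglyceride limit and then had lipid-lowering medication started or adjusted, the fallback picks the pre-adjustment value. The computed change from baseline then includes the background drug's effect.
- A subject unfasted at Visit 1 may have no Visit 1 FPG at all. The rule then declares baseline missing for a key secondary endpoint even though a fasting pre-dose value was drawn.

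At stake are the accuracy of within-arm change and a little precision.

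**Working it through.** The plan gives no figure on this point to reproduce. The check sets the rules side by side and then gauges scale.

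**1. What exists for a no-washout subject** (Section 6.0 with footnotes x and z; Section 7.1.5.4.3)

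| Measure | Visit 2 value | Passed over by the fallback? |
|---|---|---|
| Body weight, FPG | All subjects | Yes |
| Blood pressure, heart rate | All subjects | Yes, but Visit 3 values are needed to randomize (Section 5.1.3), so rarely invoked |
| A1C | Only if Visit 2 is >2 weeks after Visit 1 | Yes, in those subjects only |
| Triglycerides | Only if the Visit 1 limit was failed | Yes, in those subjects only |
| LDL, HDL | None; the flow chart's first lipid panel is at Visit 3 | No |

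Appendix 12.4 maps visits to weeks but supplies no other baseline rule.

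**2. Interval for adjusted subjects.** The regimen must be stable for at least 4 weeks before Visit 3, and the run-in is 2 weeks. So the change falls at least 4 − 2 = 2 weeks before Visit 2. A change prompted by a triglyceride result must wait for that result, so Visit 2 is then more than 2 weeks after Visit 1. A Visit 2 A1C is drawn and also sets the stratum.

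**3. Triglycerides.** Tables 3 and 4 set the exclusion limit at >600 mg/dL. An adjusted subject therefore has Visit 1 >600 and Visit 2 ≤600. The fallback takes the first. The limits fix the direction of the gap but not its size: 605 falling to 595, a gap of 10 mg/dL, satisfies both.

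**4. FPG in subjects unfasted at Visit 1.** Section 7.1.5.1 moves their FPG and fasting lipid draw to Visit 2 or earlier in place of Visit 1. If the draw is recorded under Visit 2 and Visit 3 is missing, Section 8.2.3 gives no baseline. The subject can stay in the FAS, which needs only one efficacy measurement, but leaves the per-protocol FPG analysis, which requires a baseline (Section 8.2.4.1).

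**5. Number of subjects.** The documents give no rates. Assumptions: monotherapy share 50-100%, Visit 3 value missing 1-5%, extended screening 5-30% of monotherapy subjects.

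- A1C = 160 × monotherapy share × missing × extended. Low: 160 × 0.50 × 0.01 × 0.05 = 0.04. High: 160 × 1.00 × 0.05 × 0.30 = 2.4.
- Weight and FPG = 160 × monotherapy share × missing. At 1-3% missing: 160 × 0.50 × 0.01 = 0.8 to 160 × 1.00 × 0.03 = 4.8. The extreme corner is 160 × 1.00 × 0.05 = 8.

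**6. Largest effect of one subject on a 40-subject arm's raw baseline mean.**

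- A1C: the Visit 1 and Visit 2 entry windows are both 7.5-10.5% (Table 1; Section 5.1.2), so the gap is at most 3.0 points. 3.0 / 40 = 0.075 points, against a design difference of 0.8.
- Weight: a change of 5% or more between Visits 1 and 2 is an exclusion. For an assumed 90 kg subject, 0.05 × 90 / 40 = 0.1125 kg, about 0.11, against a design difference of 2 kg.

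These are ceilings; a typical gap would be much smaller.

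**The case against.** The strongest reply is that little depends on this rule, and most of that reply stands.

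- For the usual monotherapy subject, Visit 2 comes about one week after Visit 1 (Section 7.1.5.2). No Visit 2 A1C is drawn and stratification also uses Visit 1, so for the primary endpoint the fallback and the stratum agree.
- A stratum taken from a different visit than baseline is normal here, since the regular baseline is Visit 3. The mismatch is a fault only where the fallback is older than the stratification value, in extended-screening subjects.
- The permitted changes are to lipid and blood-pressure drugs, at the investigator's discretion. Blood pressure must be measured at Visit 3, and LDL and HDL have no Visit 2 draw. That leaves triglycerides, a non-key endpoint analysed by robust regression (Section 8.2.5.1).

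A reader might infer that the rule credits MK-8521 with the effect of a background drug change. The documents do not support that. The fallback uses only pre-randomization data, is the same in all four arms, and feeds between-arm comparisons in a model that constrains the baseline mean to be common across arms. Nothing in the plan would make it act differently by arm.

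A reader might also infer that one rule (Visit 3, then Visit 2, then Visit 1) should replace both rows. That would harm washout subjects. Their Visit 1 value was taken on a second glucose-lowering agent, before a washout of at least 8 weeks and under a different A1C window (7.0-10.0%). Section 8.2.3 rightly treats their baseline as missing instead.

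The reply leaves the basic point untouched: weight and FPG, the two key secondary endpoints, have a Visit 2 value in every subject that the monotherapy row ignores.

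**Conclusion.** The point holds as a small inconsistency in the data rules. For monotherapy subjects with no Visit 3 value, the plan prefers an older measurement to a more recent pre-dose one, and its key (regimen) does not match the key used for stratification and repeat testing (interval).

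On the assumed rates, about 0 to 2 subjects are affected for A1C and a few for weight and FPG; eight would require 5% missing and every subject on monotherapy. One affected subject could move an arm's A1C baseline mean by at most 0.075 points. The expected consequence is some lost precision and a distorted within-arm change, clearest for triglycerides, with no expected bias between arms. The counts rest entirely on assumed missingness, monotherapy share and frequency of extended screening. The textual finding does not depend on them.

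**What to change.** Change only the monotherapy row of the table in Section 8.2.3, to this effect: *when Visit 3 is missing, take Visit 2 where it was collected; failing that, Visit 1; if there is none of these, baseline is missing.* Leave the washout row as it stands (Visit 3, then Visit 2, otherwise missing).

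The cost is one sentence. It adds no procedure or sample and uses only data already collected. Section 8.2.1 says no separate SAP will be issued, so this table is the operative rule. The change belongs in a protocol amendment made before any unblinding, and so before the interim analysis, which uses the same analysis approach.
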